This study's primary objective is to test the hypothesis that a single infusion of subcutaneous lidocaine can cause a clinically useful reduction in cancer pain within 48 hours of infusion and lasting a minimum of 7 days. A clinically useful reduction in pain is defined by either a 2-point reduction (on a 0-10 scale) in the worst pain experienced over a 24-hour period, or a $\geq 30\%$ reduction in 24-hour opioid requirement. We will use a composite endpoint of reduction in pain without increase in 24-hr opioid requirement or no decrease in pain with a $\geq 30\%$ reduction in 24-hour opioid requirement.

The secondary objectives are 1) to determine whether any significant toxicities occur as a result of the infusion. For this study significant toxicity is considered as any adverse event which either leads to the infusion being terminated, or which leads to medical intervention, such as prescribing of another medication or equivalent treatment, 2) to determine the effect of Lidocaine infusion on QOL parameters as measured by the Patient Outcome Scale (POS) Questionnaire and 3) to determine the duration of response to lidocaine infusion.

Eligibility criteria:

Male or female patients 18 years of age or older
In or outpatients referred to the BCCA PSMPC Clinics with a diagnosis of cancer
Subjects must have somatic, visceral or neuropathic pain related to cancer
Pain intensity, measured by a worst pain score over the last 72 hours of ≥ 4 on a 0-10 numerical rating scale
Must have tried at least one opioid medication without adequate response or with significant side-effects for at least one week
For those with neuropathic pain, must have also tried at least one adjuvant analgesic, such as a tricyclic (unless contraindicated) or an anticonvulsant without adequate response or with significant side-effects for at least one week
Life expectancy of > 3 months
Must be able to communicate symptoms indicating potential toxicity of Lidocaine
Must have a competent caregiver in the home overnight after each infusion
Must be willing to remain within 30 minutes of the Cancer Centre during each infusion

Exclusion criteria:

Clinically significant cardiac disease, i.e, cardiac failure, atrial fibrillation with slow ventricular rate (<60), any degree of heart block

New analgesic treatment initiated in time frame which might have effect within one week of study drug.

Hyper or hypokalemia.

Liver failure (bilirubin ≥ 25 μ mol/L).

Renal failure (eGFR <50% of normal)

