Uncontrolled hypertension (>160/90).

Hypotension (systolic < 90).

Uncontrolled seizures.

Planned initiation of chemotherapy, radiotherapy or bisphosphonates within 30 days prior to treatment with study drug.

Received an investigational drug within 30 days prior to study.

History of allergy to lidocaine or other topical, local or infusional anesthetics.

Methods

Recruitment

Subjects will be recruited from the BCCA Pain and Symptom Management/ Palliative Care (PSMPC) clinics at 5 sites - Vancouver, Kelowna, Abbotsford, Centre for the North and Fraser Valley. All patients attending BCCA PSMPC clinics complete a detailed pain and symptom and palliative care assessment. This includes worst pain intensity over the last 3 days as well as pain impact on function, and a body map to indicate location of pain. All patients attending the PSMPC clinics at the Vancouver and Kelowna Centres will be screened for eligibility by the research nurse and attending physician and then approached either by the attending physician or the clinic nurse as to whether or not they would like to hear about the study. If they would, the physician or research nurse will give the subject the consent form. The subject will be given the opportunity to thoroughly review and ask any questions they may have. Potential subjects from the Abbotsford and Fraser Valley sites will be approached by a Pain and Symptom Management/Palliative Care Team physician or nurse at those sites and referred to Vancouver for completion of study procedures, including consent and treatment. Once the consent is signed blood will be drawn for creatinine/GFR, bilirubin level, electrolytes if not already done in the 30 days prior to recruitment.

Baseline Visit

The baseline visit will include: documenting of age, gender, weight, history and physical, cancer diagnosis, (PPS), Edmonton Classification System for Cancer Pain (ECS-CP), medication and allergy history, blood pressure, pulse rate and ECG result, and physician assessment of cause(s) of pain(s). Patients will complete BPI, POS questionnaires and will be given a Medication Use Log to record their pain medication use for 3 days prior to their treatment day. Subjects will be introduced to the Brief Pain Inventory (BPI) at this time. This is a widely accepted and validated pain

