assessment tool which asks for pain severity over the 24 hours prior to completion, which makes it very suitable for repeated use in assessing response to lidocaine. It takes only a few minutes to complete. The pain assessment on the morning of the infusion will be the baseline point for determination of response in the study, but subjects will need to be familiar with it in order for repeated scoring throughout the study. Introducing the BPI at the baseline visit will allow it to be explained without the time pressure of needing to start the infusion.

At the baseline visit the subjects will be instructed as to discontinuation of their long-acting opioid on the morning of treatment as appropriate for the pharmacokinetics of the particular opioid: For those on Morphine, Oxycodone or Hydromorphone their long-acting dose will be omitted on the morning of the treatment, and the dose divided into three 4-hourly doses of the short-acting preparation of the same drug. In the absence of a response to treatment, the long-acting dose will be re-assessed at the end of the treatment day. If the subject does experience analgesia from the study drug then the dosing of the long-acting opioid will be adjusted as needed according to that response by telephone advice from the study physician.

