This will be arranged within a minimum of 48 hours and maximum of three weeks of the pain returning to baseline but will be no earlier than 48 hours after the 1st treatment. The baseline weight will be used to determine the dose for the second treatment. At 1000 am on Day 2 and Day 3 post second treatment, the BPI and POS will be completed. If there is a reduction in pain scores, the BPI and POS will continue to be completed on Day 7, 14 and 21 post each infusion, or until the worst pain score on the BPI #3 has returned to baseline, at which time the end of study visit will be arranged within a minimum of 48 hours and a maximum of three weeks of the pain returning to baseline. If there is no change, the questionnaires for Day 7 will be completed and the patient will be scheduled for the end of study visit within a minimum of 48 hours and maximum of three weeks of the pain returning to baseline. The Medication Use Log is to be completed daily, and the Adverse Events Log completed if an adverse event occurs. Telephone contact will be made at a minimum twice a week until the pain is back to the pre-treatment level. Subjects will also be encouraged to call the physician at any time if they experience any adverse event or to report return to baseline pain score.

Final Visit Post Second Infusion (once the worst pain score on the BPI (question #3) has returned to baseline by phone assessment and at least 48 hours or a maximum of three weeks of the pain returning to baseline., At this visit subjects will again complete the Brief Pain Inventory and POS and their Medication Use Log and Adverse Events Log will be reviewed. This will be the end of the study.

Outcome measures:

Primary:

The primary outcomes measure is a binary variable indicating whether lidocaine caused a reduction in cancer pain within 48 hours of infusion and lasting a minimum of 7 days. Lidocaine will be considered to have caused reduction in cancer pain if the subject had either one of the following episodes lasting a minimum of 7 days:

- 1) A 2-point reduction in severity of pain as assessed by the worst pain score in the last 24 hours (question 3) of the Brief Pain Inventory – Short Form (BPI), compared to the BPI pain score at baseline.

Or:

- 2) ≥30% reduction in 24-hour opioid dose.

The duration of the pain reduction is measured by weekly BPI pain scores.,

Secondary:

- 1) Incidence and severity of adverse events.

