Prior to the First Scheduled Treatment:

Medication Use Log use for three days prior to the first treatment visit

Day 1 pre each infusion:

BPI, POS, and Medication Use Log, review of Adverse Events Log, vital signs, attach Holter Monitor. The Holter Monitor will record for the duration of each infusion plus 4 hours subsequently, and will be removed by the patient.

During each infusion:

Vital signs will be measured and the infusor will be inspected every 15 minutes for the 1st hour, halfway through the infusion and on completion; the physician will be contacted ASAP if the pulse drops to less than 60 beats per minute or increases to over 100 beats per minute, or the PaO₂ falls below 90%; systolic BP changes by 25mm from pre-treatment BP. Patients will be given a Medicaton Log and an Adverse Event Log to keep track of any A/Es they experience.

In the hour prior to completion of each infusion (i.e. 4.5 to 5.5 hours since started: no later than between 2.00 and 3.00pm):

A lidocaine blood level will be drawn at the appropriate BCCA laboratory and the subject's vital signs will be taken. Blood will be analysed at the Provincial Toxicology Lab, Vancouver

At the end of each infusion on Day 1:

BPI, POS, Medication Use Log, assessment of toxicity via Adverse Events Log and vital signs.

At each of the intervals where the vital signs are to be taken, the patient's pain score will be assessed and recorded and the infusion site will be assessed to ensure the medication is infusing properly

Daily During Study:

Medication Use Log

Subjects encouraged to call study physician if any concerns
On day 2 and 3 after each Infusion and at least twice a week
or until pain is back to pre-treatment level

Phone call by physician or study nurse to review opioid dosing, adverse events and subject's perception of pain relief

Once pain returned to baseline, once weekly telephone contact will be done til the 2nd treatment visit to review any condition or medication changes

At 10.00am on Day 2 and Day 3 post each infusion, BPI and POS Questionnaires to be completed.

If there is a response to the treatment, the patient will also complete them on Day, 7, 14 and 21, or until the worst pain score on the BPI #3 has returned to baseline . If there is not a response , the BPI and POS Questionnaires will only be required for Day 2, 3 and 7.

Daily

Medication Use Log to be completed and Adverse Events Log if subject experiences symptoms or side-effects

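### The analgesic exclusion covers only newly started treatment, so a recent increase in an existing opioid or adjuvant can produce a period 1 response whatever was infused

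*Combined protocol and SAP*

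**What the plan says.** All references are to the combined protocol and SAP.

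- **Exclusion criteria.** The analgesic exclusion is "New analgesic treatment initiated in time frame which might have effect within one week of study drug". It concerns treatment being started, and its window is described by effect, not by dates. The other pain-related exclusion is "Planned initiation of chemotherapy, radiotherapy or bisphosphonates within 30 days prior to treatment with study drug", which does not mention opioids or adjuvants.
- **Eligibility criteria.** The opioid criterion is "Must have tried at least one opioid medication without adequate response or with significant side-effects for at least one week". It describes a past trial of an opioid. Current use, a minimum dose and a stable dose are not required.
- **Methods, baseline to first infusion.** The first treatment is booked within 14 days of the baseline visit, and randomisation takes place the day before it. The schedule asks for "Medication Use Log use for three days prior to the first treatment visit"; this records use and sets no stability condition.
- **Between Visits.** Opioid use is to be held at its baseline level between the infusions. Non-opioid analgesics and analgesic procedures may not be started or stopped during the study. The section attributes that second rule to the eligibility and exclusion criteria, which do not contain it in that form.
- **Baseline Visit.** "The pain assessment on the morning of the infusion will be the baseline point for determination of response in the study".
- **Outcome measures and Study Objectives.** Response is a 2-point fall in worst pain or "≥30% reduction in 24-hour opioid dose", lasting at least 7 days. The objectives add that a pain response means "reduction in pain without increase in 24-hr opioid requirement".
- **Statistical Considerations.** The power calculation assumes no period, sequence or carry-over effect.

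**The concern.** Patients are recruited from pain clinics with a worst pain score of at least 4, so a dose increase in the days before the first infusion is plausible. Nothing in the criteria as written keeps such a patient out.

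If the increase is still taking effect after the morning baseline, worst pain may fall by 2 points within 48 hours and stay down for 7 days, whichever product was infused. That happens in period 1 only. In a patient given placebo first, it can turn a non-responder into a placebo-only responder, or turn a true lidocaine-only responder into a responder to both. McNemar's test draws all its information from discordant pairs, so both changes cost power. The stake is the trial's ability to detect the effect it was sized for.

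**Working it through.** **Inputs from Statistical Considerations.** Placebo response is 30% and the difference is 20 points, so lidocaine response is 50%. Of lidocaine non-responders, 0.01% respond to placebo. There are 40 completers, with one-sided tests at 0.00153 after 20 patients and 0.02347 at the end.

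**Response types implied by the plan.**

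- Placebo only: R = 0.0001 × 0.50 = 0.00005
- Lidocaine only: L = 0.20 + R = 0.20005
- Neither: N = 0.50 − R = 0.49995

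**Reproducing the plan's figure.** Exact one-sided McNemar power with 40 pairs at 2.5% is 83.8%, against 84% stated. Using the two looks also gives 83.8%. Dropout: 40 / (1 − 0.20) = 50, as stated.

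**Adding recent dose changes (assumption).** Let a share t of patients, independent of response type, respond in period 1 because of a recent dose change. Assume equal numbers in each sequence.

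- Lidocaine first: lidocaine-only = L + N·t; placebo-only = R(1 − t)
- Placebo first: lidocaine-only = L(1 − t); placebo-only = R + N·t
- Averaged: p10 = L + 0.5t(N − L); p01 = R + 0.5t(N − R)
- Net difference: p10 − p01 = 0.20 − 0.10t

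Example, t = 0.05: p10 = 0.20005 + 0.025 × 0.2999 = 0.2075; p01 = 0.00005 + 0.025 × 0.4999 = 0.0125; difference 0.195.

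| t | p10 | p01 | Difference | Exact two-look power |
|---|---|---|---|---|
| 0 | 0.2001 | 0.0001 | 0.200 | 83.8% |
| 2% | 0.2030 | 0.0050 | 0.198 | 79.3% |
| 5% | 0.2075 | 0.0125 | 0.195 | 73.0% |
| 10% | 0.2150 | 0.0250 | 0.190 | 63.6% |
| 20% | 0.2300 | 0.0500 | 0.180 | 48.4% |

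**Where the loss comes from, at t = 5%.** If the difference shrinks to 19.5 points with no placebo-only responders, power is 81.9%. If the full 20 points are kept and 1.25% are placebo-only responders, power is 75.1%. The second component dominates. At the final look, six lidocaine-only pairs are enough when there is no reversal (one-sided p = 0.0156). One reversal raises the requirement to eight (8 of 9, p = 0.0195; 7 of 8 gives 0.035).

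**Direction.** If lidocaine had no effect (L = R), the averaged formulas give p10 = p01 for every t. The disturbance does not favour either treatment.

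**The case against.** Several parts of the case against stand, and they limit the point.

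- **The exposure is narrower than 14 days.** Response is measured from pain on the morning of infusion, so a dose change that has already acted is in the baseline. Only an effect still developing after that morning matters, and it must reach 2 points and last 7 days.
- **The power loss largely measures another weakness.** The plan assumes almost no placebo-only responders, and any source of about 1% reversal, such as ordinary variation in pain, would cost a similar amount. The assumed 30% placebo response may also already include some co-analgesic effect. No value of t is in the documents.
- **A check on order is planned.** Statistical Considerations specifies a score test of treatment order. It may detect a period effect, but the plan does not say what follows if it does, and it does not restore lost power.
- **A site might read a dose increase as new treatment.** The text does not say so, and sites reading one criterion differently is itself a reason to clarify it.

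Three stronger readings are tempting, and the documents do not support them.

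- **That the result would be biased toward lidocaine.** Random order spreads the effect over both treatments, as the working shows.
- **That patients taking no opioid undermine the endpoint.** The endpoint is either/or, so they can still respond on pain, and the opioid limb is unavailable to them in both periods. This may cost sensitivity but does not favour either treatment. The opioid instructions also presume current use, though they do not require it.
- **That the one-week inclusion rule contradicts the exclusion.** A patient must satisfy both: a minimum past trial, and no recent start that might still act. What remains is an undated window.

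**Conclusion.** The point holds as a gap in the exclusion wording. As written, the plan admits a patient whose existing opioid or adjuvant was increased just before infusion 1, and a continuing effect of that increase can be scored as a period 1 response to either product. The consequence is noise and a period effect that the sample size section assumes absent.

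The size is illustrative: power of about 79%, 73% or 64% if t is 2%, 5% or 10%, against 84% planned. This rests on the plan's own response types, equal sequences, exact testing at both looks, and t independent of response type. Because the plan starts from almost no placebo-only responders, even t = 2% takes power just below 80%. The correction is worth making because it is cheap, not because a large t has been shown.

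**What to change.** Extend the analgesic exclusion to treatment initiated **or dose changed** before the first infusion, apart from the protocol's own treatment-day opioid switch. Keep the effect-based window. Replacing it with the three log days would admit an adjuvant started four days earlier and still taking effect, which the present wording bars. The sponsor should set the window's length.

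Check the criterion against the three-day Medication Use Log before randomisation. If the window is longer than the log, use the baseline medication history and a question to the patient as well. Where a dose changed, rebook inside the 14-day limit.

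Do not simply apply the same rule before the second infusion. Between Visits and Second Treatment Visit allow that infusion from 48 hours after pain returns to baseline, when opioids may still be being restored to the earlier regimen. The sponsor should reconcile the new wording with those sections.

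Two clarifications belong with this change. Take the opioid baseline from the log already collected, since the plan fixes a baseline time for pain but not for opioid dose. State that patients with a zero opioid baseline are scored on the pain limb alone.

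The cost is wording and a check on data mostly collected already. Some first infusions will be delayed by a few days, and a few patients may be excluded.

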After the baseline visit, subjects will be scheduled for their first treatment within 14 days, and instructions sent to pharmacy accordingly. On the day prior to first treatment the subject will be randomized according to a predetermined schedule held in the dispensing pharmacy in a double-blind fashion to either placebo (D5W) or active drug (10 mg/kg preservative-free lidocaine). Both products will be administered subcutaneously via a Baxter infusor. All infusions will be made up to the same volume with D5W by a licensed pharmacist. The infusors are designed to deliver the whole contents at a constant rate over 5.5 hours, so the actual dose rate will vary depending on the subject's body weight.

Prior to the First Scheduled Treatment:

Subjects will be asked to complete a Medication Use Log for three days prior to the first treatment visit

First Treatment Day

On the day of infusion any long-acting opioid medication will be switched to short-acting as described above, because a dramatic response to lidocaine could theoretically reduce pain such that symptoms of opioid toxicity such as sedation could arise if the opioid dose was large. If this does occur the short-acting opioid dose can be reduced. It should be noted that this problem has only been seen in in-patients on high dose opioids and has not been observed in our experience with intravenous lidocaine infusions in ambulatory patients.

Subjects will be met by the study nurse who will complete the Day 1 assessment, including the Brief Pain Inventory, POS and Medication Use Log and a Holter monitor will be attached by a cardiology technician. The preferred location of insertion of the subcutaneous catheter (usually the abdomen) will be injected with 1ml of 1% lidocaine subcutaneously at least 2 minutes before insertion of the subcutaneous catheter in order both that the catheter insertion will be painless, and also for blinding, as the lidocaine infusion will produce a degree of numbness in the area once the infusion is started, whereas the placebo infusion (D5W) will not. The amount of lidocaine in 1ml of 1% solution is only 10mg, and will not cause

any systemic analgesia. The infusion (lidocaine or D5W placebo) will start between 0900 - 0930hrs.

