At 1000 am on Day 2 and Day 3, the BPI and POS will be completed. If there is a reduction in pain scores, the BPI and POS will continue to be completed on Day 7, 14 and 21 post each infusion, or until the worst pain score on the BPI #3 has returned to baseline. If there is no change, the questionnaires for Day 7 will be completed and the patient will be scheduled for the next follow up visit and treatment within a minimum of 48 hours and maximum of three weeks of the pain returning to baseline. The Medication Use Log is to be completed daily, and the Adverse Events Log completed if an adverse event occurs. Telephone contact will be made at a minimum twice a week until the pain is back to the pre-treatment level by the research nurse or physician and to adjust medications if necessary, and, once pain returned to baseline, once weekly telephone contact will be done til the 2nd treatment visit to review any condition or medication changes. Subjects will also be encouraged to call the physician at any time if they experience any adverse event or to report return to baseline pain score.

Once the worst pain score on the BPI (question #3) has returned to baseline and at least 48 hours have elapsed, the second treatment will be arranged. If there is a response the patient will continue with diaries and questionnaires weekly until the BPI score returns to baseline

Second Treatment Visit

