- 2) Effect of Lidocaine infusion on QOL parameters as measured by the Patient Outcome Scale (POS) Questionnaire
- 3) Duration of response to lidocaine infusion.

Notes on Outcome Measures

The BPI refers to “worst pain over the last 24 hours” rated between 0 and 10, and a 2 points difference has been determined in multiple studies to be clinically useful. Based on our experience with lidocaine infusions already we know that a response to lidocaine occurs within the first 3 days (actually usually within the first 24 hours), so the daily BPI for the first 3 days will capture whether or not a clinically significant improvement in pain has been achieved.

Because some patients may accept similar levels of pain but reduce their opioid analgesics significantly, with consequent reduction in side-effects, the 30% reduction in analgesic use is also included as indicative of a positive response, to ensure that clinically meaningful benefits are not missed by relying just on the pain scores.

For this study significant toxicity is considered as any adverse event which either leads to the infusion being terminated, or which leads to medical intervention, such as prescribing of another medication or equivalent treatment.

The Patient Outcome Scale (POS) is a QOL tool used routinely in the BCCA PSMPC clinics that addresses physical, psychological, spiritual, practical, psychosocial and emotional concerns and consists of 12 questions in 9 domains: pain, other symptoms, anxiety, information, support, depression, self-worth, wasted time and personal affairs. It was used in the Subcutaneous Lidocaine Feasibility Study.

The duration of response is a descriptive outcome which will be determined by the time to return of the BPI question #3 worst pain in 24 hours pain rating to the same as at that provided on the morning of the infusion, before the infusion started. The duration of benefit will be reported in descriptive terms only and is not an endpoint which will be subject to statistical analysis. This data will be useful for planning subsequent clinical implementation, if the study shows the treatment to be effective.

Schedule of Assessments:

Baseline:

Age, gender, weight, history and physical, cancer diagnosis, Palliative Performance Scale (PPS), and Edmonton Classification System for Cancer Pain (ECS-CP), physician assessment of cause(s) of pain(s), medication and allergy history, blood pressure, pulse rate and ECG, BPI, POS and blood draw if needed.

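### The potassium, bilirubin and eGFR exclusions are checked once, at recruitment, and not again before either infusion; the gap is widest at infusion 2

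*Combined protocol and SAP*

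**What the plan says.** The Exclusion criteria list hyper- or hypokalemia, raised bilirubin and reduced eGFR, with no date by which each must be known. The Recruitment section under Methods gives the only instruction to measure them: after consent, "blood will be drawn for creatinine/GFR, bilirubin level, electrolytes if not already done in the 30 days prior to recruitment". The Baseline entry in the Schedule of Assessments has the same conditional test: "blood pressure, pulse rate and ECG, BPI, POS and blood draw if needed".

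Timing after that is set in three places:

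- Baseline Visit: "subjects will be scheduled for their first treatment within 14 days".
- Between Visits, for a subject who has not responded: "If there is no change, the questionnaires for Day 7 will be completed".
- Second Treatment Visit, for the window: "This will be arranged within a minimum of 48 hours and maximum of three weeks of the pain returning to baseline". The same section adds a floor counted from infusion 1: "but will be no earlier than 48 hours after the 1st treatment".

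The Day 1 list that applies before each infusion reads: "BPI, POS, and Medication Use Log, review of Adverse Events Log, vital signs, attach Holter Monitor". It contains no chemistry and no eligibility check. The one blood test on a treatment day is a lidocaine level in the last hour of the infusion. Between infusions, once pain is back to baseline, "once weekly telephone contact will be done til the 2nd treatment visit to review any condition or medication changes".

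**The concern.** An exclusion based on a laboratory value protects the subject only if the value is current when the drug is given. Here the clock runs from recruitment, while the exposure comes later. A subject whose potassium, bilirubin or renal function has crossed a limit since the test, without symptoms and without anyone noticing, could receive 10 mg/kg of lidocaine with every stated step followed.

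The plan does tie another exclusion to dosing: planned chemotherapy, radiotherapy or bisphosphonates are judged over the 30 days before study drug. Chemistry is not treated in that way. Eligibility asks only for a life expectancy above three months, so a value from one or two months ago cannot be presumed to still hold.

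What is at stake is subject safety. The primary comparison does not depend on it.

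**Working it through.** The plan states no figure for the age of results at dosing, so there is none to reproduce. The ages follow from adding the stated windows.

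**Inputs**

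- Age of results at recruitment: 0 days if drawn at consent, up to 30 if already on file (Recruitment).
- Gap from consent to baseline visit, g: not stated. Taken as 0, with 14 as a sensitivity case.
- Baseline visit to infusion 1: up to 14 days (Baseline Visit).
- Infusion 1 to return of baseline pain: 7 days if judged at the Day 7 questionnaire, 21 if at Day 21 (Between Visits). A longer response has no stated limit.
- Return of pain to infusion 2: up to 21 days (Second Treatment Visit).

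**Formulas**

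- Maximum age at infusion 1 = age at recruitment + g + 14.
- Maximum age at infusion 2 = maximum age at infusion 1 + days to return of pain + 21.

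**Results, g = 0**

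| | Drawn at consent | On file, 30 days old |
|---|---|---|
| Infusion 1 | 0 + 14 = 14 | 30 + 14 = 44 |
| Infusion 2, pain back by Day 7 | 14 + 7 + 21 = 42 | 44 + 7 + 21 = 72 |
| Infusion 2, pain back by Day 21 | 14 + 21 + 21 = 56 | 44 + 21 + 21 = 86 |

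For a subject with no response at all, the three weeks might instead be counted from infusion 1. The infusion 2 limits are then 14 + 21 = 35 and 44 + 21 = 65 days.

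**Sensitivity to g.** With g = 14, every entry rises by 14. Results on file reach 58, 86 and 100 days; results drawn at consent reach 28, 56 and 70.

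**Shortest ages, g = 0.** The three-day medication log before infusion 1 gives 3 days (drawn at consent) or 30 + 3 = 33 days (on file, 30 days old). The 48-hour minimum before infusion 2 gives 3 + 2 = 5 and 33 + 2 = 35 days. If the Day 7 questionnaire comes first, these are 3 + 7 = 10 and 33 + 7 = 40.

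**What a 30-day limit would change.** At infusion 1, nothing for blood drawn at consent (14 days, or 28 with g = 14). For results on file the maximum falls from 44 to 30 days. At infusion 2, the maxima of 42 to 86 days all fall to 30.

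**Cost in pairs.** A second infusion that is withheld loses a pair. The plan enrols 50 to keep 50 × (1 − 0.20) = 40. If 2% to 10% of 40 pairs were withheld (an assumed range, since the documents give none), that is 0.8 to 4 pairs. Under the plan's assumptions an exact one-sided McNemar test at 2.5% needs at least 6 discordant pairs, all favouring lidocaine (0.5^6 = 0.0156; 0.5^5 = 0.031). P(Bin(n, 0.20) ≥ 6) is 0.839 at n = 40, matching the stated 84%; 0.800 at 38; and 0.754 at 36. Those reductions apply only if other losses have already used up the ten-patient allowance.

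**The case against.** The strongest reply is that the risk is small and already guarded.

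- For infusion 1 the plan is close to adequate. Fresh results are at most 14 days old when consent and baseline coincide. This stands, and it is why the point is mainly about infusion 2.
- Each subject receives lidocaine once. Infusion 2, where results are oldest, is placebo for those given lidocaine first. This also stands: exposure on the oldest results is confined to the placebo-first sequence.
- Safeguards during infusion are real: vital signs and infusor checks every 15 minutes in the first hour, a mid-infusion return, a 30-minute travel limit, defined triggers for calling the physician, and a physician on site. Subjects must be able to report toxicity. These can limit harm once it appears, but none of them measures chemistry. The weekly calls can pick up only a change that is known or felt.
- Clinical experience is reassuring: over 3000 subcutaneous infusions without toxicity problems, intravenous use in cancer pain at 5–9 mg/kg over 1–2 hours, and two hospice series with no significant adverse effects attributed to lidocaine. The subcutaneous experience is in a largely non-cancer population at 1.5 mg/kg/hr, against 10/5.5 = 1.82 here; the intravenous rates are higher, from 5/2 = 2.5 to 9/1 = 9. The documents do not say how many of these patients had abnormal potassium, bilirubin or renal function, so the experience lowers concern without settling it.

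Three stronger readings are tempting, and the documents support none of them. A reader might infer that staff are directed to treat someone known to meet an exclusion; nothing says so. A reader might infer that results will usually be two months old; the figures above stack every window at its limit, and typical ages cannot be estimated. A reader might infer that an exclusionary finding such as heart block on the first Holter would not reach the study physician before infusion 2. The tracing is analysed the day after recording and reviewed independently. The protocol is only silent on who is told, and reporting lines may be set out elsewhere.

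**Conclusion.** The gap holds on the text. Three laboratory exclusions are verified once, by a rule tied to recruitment, and no re-check is required before either dose. With consent and baseline on the same day, results can be up to 14 days old (fresh) or 44 days old (on file) at infusion 1. At infusion 2 they can be up to 42 or 72 days old if pain returns by Day 7, and 56 or 86 days if by Day 21. Later returns extend this without a cap, and so does any gap between consent and baseline.

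These are permitted maxima, not expected values. The number of subjects affected cannot be estimated, because the documents give neither a rate of crossing a limit nor a rate of harm if one is crossed. The case rests on the plan's own decision that these values should exclude a patient. The primary analysis is unaffected. This is a minor safety improvement, mainly for infusion 2 in placebo-first subjects.

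**What to change.** Time the chemistry to dosing:

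- Require creatinine/GFR, bilirubin and electrolytes within 30 days before each infusion, accepting routine-care results. The 30 days is a proposed limit; the plan sets none for chemistry before dosing.
- For infusion 1, draw at the consent or baseline visit whenever the existing result would be over 30 days old on the scheduled date. A result no more than 30 − 14 = 16 days old at the baseline visit always qualifies. This avoids an extra trip and allows review before randomisation, which takes place the day before treatment.
- For infusion 2, obtain and review a result before dosing if none falls within 30 days.
- Add re-confirmation of the safety exclusions to the Day 1 list before each infusion.
- Optionally, state that an exclusionary finding on the first Holter goes to the study physician before infusion 2, worded so that it does not suggest the treatment given.

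The cost is protocol wording, one routine blood test for some subjects, possibly an extra visit before infusion 2 (a real burden for subjects referred from other sites), and a few withheld second infusions. The 20% drop-out allowance can absorb those unless other losses use it up, so withheld subjects should be counted and replaced if needed.
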